5.8 General Concomitant Medication and Supportive Care Guidelines

Medications or vaccinations specifically prohibited in the exclusion criteria are not allowed during the ongoing trial. If there is a clinical indication for one of these or other medications or vaccinations specifically prohibited during the trial, discontinuation from trial therapy or vaccination may be required. The final decision on any supportive therapy or vaccination rests with the investigator and/or the subject's primary physician.

5.8.1 Acceptable Concomitant Medications

All treatments that the investigator considers necessary for a subject's welfare may be administered at the discretion of the investigator in keeping with the community standards of medical care. All concomitant medication will be recorded on the case report form (CRF) including all prescription, over-the-counter (OTC), herbal supplements, and IV medications and fluids. If changes occur during the trial period, documentation of drug dosage, frequency, route, and date may also be included on the CRF. All concomitant medications received within 28 days before the first dose of trial treatment and 30 days after the last dose of trial treatment should be recorded.

5.8.2 Prohibited Concomitant Medications

Subjects are prohibited from receiving the following therapies during the Screening and Treatment Phase (including retreatment for post-complete response relapse) of this trial:

- Immunotherapy not specified in this protocol
- Chemotherapy not specified in this protocol
- Investigational agents other than pembrolizumab
- Radiation therapy not specified in this protocol

Note: palliative radiation therapy to a symptomatic solitary lesion or to the brain may be allowed at the investigator's discretion after discussion with sponsor.

- Live vaccines within 30 days prior to the first dose of trial treatment and while participating in the trial. Examples of live vaccines include, but are not limited to, the following: measles, mumps, rubella, varicella/zoster, yellow fever, rabies, BCG, and typhoid vaccine.

Systemic glucocorticoids for any purpose other than to modulate symptoms from an event of clinical interest of suspected immunologic etiology. The use of physiologic doses of corticosteroids may be approved after consultation with the Sponsor.

Subjects who, in the assessment by the investigator, require the use of any of the aforementioned treatments for clinical management should be removed from the trial. Subjects may receive other medications that the investigator deems to be medically necessary.

There are no prohibited therapies during the Post-Treatment Follow-up Phase.

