5.7 Subject Compliance Monitoring

Subjects who are significantly non-compliant with protocol required visits, assessments, and dosing instructions may be withdrawn from the study by the investigator and/or sponsor. The investigator and/or sponsor have the right to discontinue a subject from study treatment or withdraw a patient from the study at any time.

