5.7.1 Criteria for Taking a Participant Off Study

Participants will be removed from study when any of the following criteria apply:

- Lost to follow-up
- Withdrawal of consent for data submission
- Death

The reason for taking a participant off study, and the date the participant was removed, must be documented in the case report form (CRF).

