5.9.1 Pregnancy

If a subject inadvertently becomes pregnant while on treatment with pembrolizumab, the subject will immediately be removed from the study. The site will contact the subject at least monthly and document the subject's status until the pregnancy has been completed or terminated.

It must be reported immediately to the regulatory specialist, research coordinator, and [contact] in accordance with the procedures described below. Pregnancy in itself is not regarded as an adverse event unless there is a suspicion that the investigational product may have interfered with the effectiveness of a contraceptive medication. This will be reported to the IRB if necessary.

The outcome of the pregnancy will be reported to Merck without delay and within 2 working days if the outcome is a serious adverse experience (e.g., death, abortion, congenital anomaly, or other disabling or life-threatening complication to the mother or newborn).

When a pregnancy has been confirmed, the following procedures should occur:

- The investigator must notify the sponsor immediately.
- The study drug must be discontinued immediately.
- The subject must be withdrawn from the study.
- The EOT visit evaluations must be performed.

The study investigator will make every effort to obtain permission to follow the outcome of the pregnancy and report the condition of the fetus or newborn to NYULMC. If a male subject impregnates his female partner the study personnel at the site must be informed immediately and the pregnancy reported to NYULMC and to Merck and followed as described above and in Section 10.2.2).

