6.6.9.5 Survival Follow-up

Once a subject experiences confirmed disease progression or starts a new anti-cancer therapy, the subject moves into the survival follow-up phase and should be contacted by telephone every 12 weeks to assess for survival status until death, withdrawal of consent, or the end of the study, whichever occurs first.

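### Sections 5.8.2, 5.7 and 5.9.1 take participants off the study for reasons that 5.7.1 does not list and that conflict with the follow-up sections; if follow-up stops at removal, PFS and OS could be informatively censored

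*Combined protocol and SAP*

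**What the plan says.** **Exits from the study**

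- Section 5.8.2: participants who "require the use of any of the aforementioned treatments for clinical management should be removed from the trial". The list covers non-protocol immunotherapy, chemotherapy and radiation, other investigational agents, live vaccines, and systemic glucocorticoids given for anything other than a suspected immune event. A note allows some palliative radiation, including to the brain, after discussion with the sponsor. Physiologic steroid doses may be approved.
- Section 5.7: significantly non-compliant participants "may be withdrawn from the study by the investigator and/or sponsor". The investigator and sponsor also "have the right to discontinue a subject from study treatment or withdraw a patient from the study at any time".
- Section 5.9.1: on pregnancy, "the subject will immediately be removed from the study", and again, "The subject must be withdrawn from the study".

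**Off-study list**

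- Section 5.7.1: "Participants will be removed from study when any of the following criteria apply". It then names loss to follow-up, withdrawal of consent to submit data, and death.

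**Text pointing to continued follow-up**

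- Section 5.8: where a prohibited medication is needed, "discontinuation from trial therapy or vaccination may be required".
- Sections 5.11 and 6.6.9.4: those who stop treatment for a reason other than progression have disease-status follow-up.
- Section 6.5.2: those who start a new anti-cancer therapy move to survival follow-up.
- Section 6.6.9.5: after confirmed progression or new anti-cancer therapy, the participant "should be contacted by telephone every 12 weeks to assess for survival status until death, withdrawal of consent, or the end of the study".

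**Analysis**

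- Section 8.1.6 censors PFS at the last disease evaluation and OS at the date last known alive.
- Section 3.3 compares the medians with historical values of 5.4 months (PFS) and 9.5 months (OS).

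**The concern.** The protocol treats leaving therapy (5.9) and leaving the study (5.7.1) as different events, and 5.7 names study treatment and study as separate options. A site may therefore read removal from the trial in 5.8.2 as the end of data collection. Some of the triggers plausibly accompany clinical decline: systemic steroids for a non-immune reason, radiation the sponsor has not approved, and non-compliance. If outcome collection stops there, 8.1.6 censors these participants just before a period of higher risk, and the Kaplan-Meier curve is too high. The medians are set against fixed historical values with no concurrent control, so any upward bias would read as benefit. The statistical plan in section 9 has no rule or sensitivity analysis for these participants.

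**Working it through.** **1. The passages side by side**

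| Reason for exit | Section that ends study participation | In the 5.7.1 list? | Clear route into follow-up? |
|---|---|---|---|
| New non-protocol anti-cancer drug | 5.8.2 | No | Yes for survival (6.5.2, 6.6.9.5) |
| Non-immune systemic glucocorticoid | 5.8.2 | No | Only if removal is read as stopping treatment (5.11, 6.6.9.4); no 6.6.9.5 trigger met |
| Unapproved non-protocol radiation | 5.8.2 | No | Unclear; depends on whether it counts as new anti-cancer therapy |
| Non-compliance | 5.7 (discretionary) | No | As for glucocorticoids |
| Pregnancy | 5.9.1 | No | At least monthly contact until the pregnancy ends, although the participant is off study |

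Survival follow-up under 6.6.9.5 starts at confirmed progression or new anti-cancer therapy. A participant removed for glucocorticoids or non-compliance has met neither condition, so this is where the gap is real. Section 5.9 lists inability or unwillingness to comply as a reason to end protocol therapy, while 5.7 allows withdrawal from the study for non-compliance.

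**2. The plan's own figures**

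The plan states no power, event count or precision for PFS or OS. Its one power figure, 88% for the paired PD-L1 test, reproduces: a paired t calculation with n = 12, effect size 1.0 and two-sided 0.05 gives 88.3%, and a simulated signed rank test with normal approximation gives 87.6%. It is unaffected, because the primary tissue is taken before pembrolizumab.

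**3. Possible size if follow-up stops at removal**

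Inputs from the documents: true median m = 9.5 months (OS) or 5.4 months (PFS), taking the section 3.3 historical values as the truth.

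Assumptions, not in the documents:

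- event times are exponential with hazard λ before removal and kλ after it, with k from 1 to 3;
- removal has constant hazard r = λs/(1 − s), so that a share s is removed before the event, with s from 5% to 30% (3 to 18 of the 60 planned participants).

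With complete follow-up, survival is

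S(t) = e^(−(λ+r)t) + r·[e^(−kλt) − e^(−(λ+r)t)] / (λ + r − kλ).

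Solve S(m) = 0.5 for λ. If removed participants are censored at removal, the Kaplan-Meier curve estimates e^(−λt), and its median is ln 2/λ.

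Example, OS with s = 20% and k = 2: r = 0.25λ. With λ = 0.0686 per month, (λ + r)·9.5 = 0.814 and kλ·9.5 = 1.303, so S(9.5) = 0.443 + (−1/3)(0.272 − 0.443) = 0.500. The Kaplan-Meier median is 0.693/0.0686 = 10.1 months.

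| Share removed | OS, k=1 | OS, k=1.5 | OS, k=2 | OS, k=3 | PFS, k=1 | PFS, k=1.5 | PFS, k=2 | PFS, k=3 |
|---|---|---|---|---|---|---|---|---|
| 5% | 9.50 | 9.58 | 9.64 | 9.72 | 5.40 | 5.44 | 5.48 | 5.53 |
| 10% | 9.50 | 9.66 | 9.78 | 9.96 | 5.40 | 5.49 | 5.56 | 5.66 |
| 20% | 9.50 | 9.84 | 10.11 | 10.50 | 5.40 | 5.59 | 5.75 | 5.97 |
| 30% | 9.50 | 10.06 | 10.49 | 11.12 | 5.40 | 5.72 | 5.96 | 6.32 |

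For k from 1.5 to 3, the overstatement runs from 9.58 − 9.5 = 0.08 to 11.12 − 9.5 = 1.62 months for OS, and from 5.44 − 5.4 = 0.04 to 6.32 − 5.4 = 0.92 months for PFS. It is zero at k = 1, and zero if follow-up continues after removal.

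**The case against.** The strongest reply is that removal from the trial in 5.8.2 simply means leaving treatment. Section 5.8 says so for the same situation. Section 5.8.2 limits its prohibitions to screening and treatment and lifts them in post-treatment follow-up. Section 4.6.1 asks for every effort to obtain information on those who withdraw, 4.6.2 has final-visit activities done at withdrawal, and 5.11.1 follows participants for a year after protocol therapy or until death. This shows what was probably intended and stands as such. It does not settle what a site must do: 5.7 and 5.7.1 use study as something distinct from treatment, and 4.6.1 sets no schedule.

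Three stronger readings are tempting, and the documents do not support them.

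- *That 5.7.1 is the only permitted list.* It is not worded as exhaustive, and withdrawal under 5.7 is discretionary.
- *That PFS and OS would be informatively censored.* Those starting new anti-cancer therapy go to survival follow-up, some palliative radiation is permitted, a participant with documented progression already has a PFS event, and removals for pregnancy or a live vaccine have no evident link to prognosis.
- *That OS could gain about 2 months at 20% removal.* Simulation does give a median of 11.5–11.7 months, but only if every removed participant is lost and dies on average 1–3 months later. The exponential mean is 9.5/ln 2 = 13.7 months, so that implies a hazard about 4.6 to 14 times the average (13.7/3 to 13.7/1). The result is close to the ceiling 9.5/(1 − 0.20) = 11.9 months. Nothing in the documents supports those inputs.

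**Conclusion.** The contradiction in wording stands. Sections 5.8.2, 5.7 and 5.9.1 end study participation for reasons outside the 5.7.1 list, against 5.8 and the follow-up sections, and no section states what follow-up then applies. Informative censoring is a conditional risk, confined mainly to participants removed for non-immune systemic glucocorticoids, unapproved non-protocol radiation or non-compliance. Any overstatement of the medians lies within the ranges in the working, and those rest on an assumed removal share and an assumed excess hazard. PFS and OS are secondary endpoints without a powered test, so this is a matter to correct and does not undermine the trial's main question. Censoring of PFS when a participant starts another cancer therapy (5.11, 6.6.9.4 and 8.1.6) is a separate matter: it arises whatever 5.8.2 says.

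**What to change.** - In 5.8.2 and 5.7, distinguish *off protocol therapy* from *off study*. State that these participants remain in the existing disease-status and survival follow-up (6.6.9.4 and 6.6.9.5) unless a 5.7.1 reason applies, and that this includes those with neither progression nor new therapy. Whether and when treatment ends stays with the sponsor.
- In 5.9.1, reconcile withdrawal from the study with the continued contact that section requires, and keep survival-status contact. No imaging needs to be prescribed.
- The sponsor should reconcile the scope of the glucocorticoid restriction in 5.8.2 with the chemotherapy premedication mentioned in 5.5.5, which names no agents, and with the brain radiation allowed in 5.11.2.

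The cost is wording in three sections, the sponsor's reconciliation of the glucocorticoid text, and visits and calls already in the schedule for those affected. The change should be made while participants are still being followed, because outcomes not collected after removal may not be recoverable at analysis.

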5.8.3 Supportive Care Guidelines

Subjects should receive appropriate supportive care measures as deemed necessary by the treating investigator. Suggested supportive care measures for the management of adverse events with potential immunologic etiology are outlined below. Where appropriate, these guidelines include the use of oral or intravenous treatment with corticosteroids as well as additional anti-inflammatory agents if symptoms do not improve with administration of corticosteroids. Note that several courses of steroid tapering may be necessary as symptoms may worsen when the steroid dose is decreased. For each disorder, attempts should be made to rule out other causes such as metastatic disease or bacterial or viral infection, which might require additional supportive care. The treatment guidelines are intended to be applied when the investigator determines the events to be related to pembrolizumab.

It may be necessary to perform conditional procedures such as bronchoscopy, endoscopy, or skin photography as part of evaluation of the event and should be discussed with the overall PI.

- **Pneumonitis:**

- For **Grade 2 events**, treat with systemic corticosteroids. When symptoms improve to Grade 1 or less, steroid taper should be started and continued over no less than 4 weeks.
- For **Grade 3-4 events**, immediately treat with intravenous steroids. Administer additional anti-inflammatory measures, as needed.
- Add prophylactic antibiotics for opportunistic infections in the case of prolonged steroid administration.

- **Diarrhea/Colitis:**

Subjects should be carefully monitored for signs and symptoms of enterocolitis (such as diarrhea, abdominal pain, blood or mucus in stool, with or without fever) and of bowel perforation (such as peritoneal signs and ileus).

- All subjects who experience diarrhea/colitis should be advised to drink liberal quantities of clear fluids. If sufficient oral fluid intake is not feasible, fluid and electrolytes should be substituted via IV infusion. For Grade 2 or higher diarrhea, consider GI consultation and endoscopy to confirm or rule out colitis.

- For **Grade 2 diarrhea/colitis** that persists greater than 3 days, administer oral corticosteroids.
- For **Grade 3 or 4 diarrhea/colitis** that persists > 1 week, treat with intravenous steroids followed by high dose oral steroids.
- When symptoms improve to Grade 1 or less, steroid taper should be started and continued over no less than 4 weeks.

- **Type 1 diabetes mellitus (if new onset, including diabetic ketoacidosis [DKA]) or ≥ Grade 3 Hyperglycemia, if associated with ketosis (ketonuria) or metabolic acidosis (DKA)**
 - For **T1DM or Grade 3-4 Hyperglycemia**
 - Insulin replacement therapy is recommended for Type I diabetes mellitus and for Grade 3-4 hyperglycemia associated with metabolic acidosis or ketonuria.
 - Evaluate patients with serum glucose and a metabolic panel, urine ketones, glycosylated hemoglobin, and C-peptide.

- **Hypophysitis:**
 - For **Grade 2** events, treat with corticosteroids. When symptoms improve to Grade 1 or less, steroid taper should be started and continued over no less than 4 weeks. Replacement of appropriate hormones may be required as the steroid dose is tapered.
 - For **Grade 3-4** events, treat with an initial dose of IV corticosteroids followed by oral corticosteroids. When symptoms improve to Grade 1 or less, steroid taper should be started and continued over no less than 4 weeks. Replacement of appropriate hormones may be required as the steroid dose is tapered.

- **Hyperthyroidism or Hypothyroidism:**

Thyroid disorders can occur at any time during treatment. Monitor patients for changes in thyroid function (at the start of treatment, periodically during treatment, and as indicated based on clinical evaluation) and for clinical signs and symptoms of thyroid disorders.

 - **Grade 2** hyperthyroidism events (and **Grade 3-4** hypothyroidism):
 - In hyperthyroidism, non-selective beta-blockers (e.g. propranolol) are suggested as initial therapy.
 - In hypothyroidism, thyroid hormone replacement therapy, with levothyroxine or liothyronine, is indicated per standard of care.
 - **Grade 3-4** hyperthyroidism
 - Treat with an initial dose of IV corticosteroid followed by oral corticosteroids. When symptoms improve to Grade 1 or less, steroid taper should be started and continued over no less than 4 weeks. Replacement of appropriate hormones may be required as the steroid dose is tapered.

- **Hepatic:**
 - For **Grade 2** events, monitor liver function tests more frequently until returned to baseline values (consider weekly).
 - Treat with IV or oral corticosteroids
 - For **Grade 3-4** events, treat with intravenous corticosteroids for 24 to 48 hours.
 - When symptoms improve to Grade 1 or less, a steroid taper should be started and continued over no less than 4 weeks.

- **Renal Failure or Nephritis:**
 - For **Grade 2** events, treat with corticosteroids.
 - For **Grade 3-4** events, treat with systemic corticosteroids.

- When symptoms improve to Grade 1 or less, steroid taper should be started and continued over no less than 4 weeks.

Management of Infusion Reactions: Signs and symptoms usually develop during or shortly after drug infusion and generally resolve completely within 24 hours of completion of infusion.

5.9 Criteria for Taking a Participant Off Protocol Therapy

Duration of therapy will depend on individual response, evidence of disease progression and tolerance. In the absence of treatment delays due to adverse event(s), treatment with platinum + etoposide may continue for UP TO 6 TOTAL CYCLES (on and off therapy) but may be stopped at 4 cycles at investigator discretion based on tolerability. Treatment may be stopped at any time if one of the below criteria applies. Pembrolizumab may continue for up to 34 cycles (2 years) or until one of the following criteria applies:

- Disease progression
- Intercurrent illness that prevents further administration of treatment
- Unacceptable adverse event(s)
- Participant demonstrates an inability or unwillingness to comply with the oral medication regimen and/or documentation requirements
- Participant decides to withdraw from the protocol therapy
- General or specific changes in the participant's condition render the participant unacceptable for further treatment in the judgment of the treating investigator

Participants will be removed from the protocol therapy when any of these criteria apply UNLESS THERE IS ISOLATED CNS PROGRESSION (Section 5.11.2). The reason for removal from protocol therapy, and the date the participant was removed, must be documented in the case report form (CRF). Alternative care options will be discussed with the participant.

In the event of unusual or life-threatening complications, treating investigators must immediately notify the Overall PI, [name], [contact] .

5.9.1 Pregnancy

If a subject inadvertently becomes pregnant while on treatment with pembrolizumab, the subject will immediately be removed from the study. The site will contact the subject at least monthly and document the subject's status until the pregnancy has been completed or terminated.

It must be reported immediately to the regulatory specialist, research coordinator, and [contact] in accordance with the procedures described below. Pregnancy in itself is not regarded as an adverse event unless there is a suspicion that the investigational product may have interfered with the effectiveness of a contraceptive medication. This will be reported to the IRB if necessary.

The outcome of the pregnancy will be reported to Merck without delay and within 2 working days if the outcome is a serious adverse experience (e.g., death, abortion, congenital anomaly, or other disabling or life-threatening complication to the mother or newborn).

When a pregnancy has been confirmed, the following procedures should occur:

- The investigator must notify the sponsor immediately.
- The study drug must be discontinued immediately.
- The subject must be withdrawn from the study.
- The EOT visit evaluations must be performed.

The study investigator will make every effort to obtain permission to follow the outcome of the pregnancy and report the condition of the fetus or newborn to NYULMC. If a male subject impregnates his female partner the study personnel at the site must be informed immediately and the pregnancy reported to NYULMC and to Merck and followed as described above and in Section 10.2.2).

5.9.2 Use in Nursing Women

It is unknown whether pembrolizumab is excreted in human milk. Since many drugs are excreted in human milk, and because of the potential for serious adverse reactions in the nursing infant, subjects who are breast-feeding are not eligible for enrollment.

